5.3 Subject Enrollment

Before subjects begin participation in any study-specific activities/procedures, Amgen requires a copy of the site's written institutional review board/independent ethics committee (IRB/IEC) approval of the protocol, informed consent form (ICF), and all other subject information and/or recruitment material, if applicable (see Section 11.3).

The subject or the subject's legally acceptable representative must personally sign and date the IRB/IEC and Amgen approved informed consent before commencement of study-specific procedures.

A subject is considered enrolled when the investigator decides that the subject has met all eligibility criteria. The investigator is to document this decision and date, in the subject's medical record and in/on the Subject Enrollment case report form (CRF).

Each subject who enters into the screening period for the study (defined as the point when the subject signs the ICF) receives a unique subject identification number before any study-related activities/procedures are performed. The subject identification number will be assigned manually. This number will be used to identify the subject throughout the clinical study and must be used on all study documentation related to that subject.

The subject identification number must remain constant throughout the entire clinical study; it must not be changed after initial assignment, including if a subject is rescreened.

Sites that do not enroll subjects within 6 months of site initiation may be closed.

5.4 Screen Failures

Screen failures are defined as subjects who consent to participate in the clinical study but are not subsequently enrolled in the study. A minimal set of screen failure

Protocol Number: 20200439

Date: 05 June 2024 Page 54 of 176

information will be collected that includes demography, screen failure details, eligibility criteria, and any serious adverse events.

Individuals who do not meet the criteria for participation in this study (screen failure) may be rescreened.

6. Study Intervention

Study intervention is defined as any investigational product(s), non-investigational product(s), placebo, combination product(s), or medical device(s) intended to be administered to a study subject according to the study protocol.

Note that in several countries, investigational product and non-investigational product are referred to as investigational medicinal product and non-investigational medicinal product, respectively.

A summary of the dosing and administration of each treatment is shown in Table 6-1 below.

6.1 Study Interventions Administered

6.1.1 Investigational Products

Protocol Number: 20200439

Date: 05 June 2024 Page 55 of 176

Table 6-1. Investigational Products

	Table 0-1. Investigational Froducts	
	Amgen Investigational Product: ^a	Amgen Investigational Product: ^a
Study Treatment Name	Tarlatamab	AMG 404
Dosage Formulation	Tarlatamab is supplied as a sterile, single use, preservative free lyophilized drug product containing mg of tarlatamab per vial. Tarlatamab is intended for reconstitution with sterile water for injection and dilution in an intravenous (IV) bag with normal saline (% sodium chloride) and an IV solution stabilizer. The drug product is formulated with MM L-glutamic acid, % (w/v) sucrose, % (w/v) polysorbate 80, at a final pH of	Note: As of Protocol Amendment 3, AMG 404 will not be supplied. AMG 404 is supplied in a 3 mL Type 1 glass tubing vial containing 1 mL deliverable volume of mg/mL. The drug product is formulated with mM acetate (sodium counterion), (w/v) sucrose, 0.01% (w/v) polysorbate 80, pH and will be prepared for IV administration by dilution.
Unit Dose Strength(s)/ Dosage Level(s) and Dosage Frequency	The starting dose and dosing schedule of tarlatamab will be as the target dose with 1-step dosing. Tarlatamab will be administered after the target dose is reached. If the combination of tarlatamab and AMG 404 is not tolerated (based on target DLT rate > 30%), tarlatamab dose level will be further dose reduced or the day of administration of AMG 404 in combination with tarlatamab will be adjusted.	mg
Route of Administration	IV	IV
Accountability	The total volume of preparation, dose, start date/time, stop date/time, and lot number are to be recorded on each subject's CRF(s).	The total volume of preparation, dose, start date/time, stop date/time, and lot number are to be recorded on each subject's CRF(s).
Dosing Instructions	Tarlatamab will be administered as a short-term IV infusion for 60 minutes (± 10 minutes) followed by a flush once (except in cycle 1 where 1-step-dosing will be implemented).	AMG 404 will be delivered using infusion pumps approved for use by the appropriate regulatory authority for the country in which the subject is undergoing treatment. AMG 404 solution for infusion will be prepared in bags for IV infusion and delivered through infusion lines. The drug will be administered as a short-term IV infusion at a constant flow rate over 30 minutes

CRF = case report form; DLT = dose limiting toxicity; IV = intravenous;

a Tarlatamab and AMG 404 will be manufactured and packaged by Amgen Inc. and distributed using Amgen clinical study drug distribution procedures.

Protocol Number: 20200439

Date: 05 June 2024 Page 56 of 176

6.1.2 Non-investigational Products

No non-investigational products will be administered in this study.

6.1.3 Medical Devices

No medical devices will be used in this study.

Other non-investigational medical devices may be used in the conduct of this study as part of standard care.

Non-Amgen non-investigational medical devices (eg, syringes, sterile needles), that are commercially available are not usually provided or reimbursed by Amgen (except, for example, if required by local regulation). The investigator will be responsible for obtaining supplies of these devices.

6.1.4 Other Protocol-required Therapies

All other protocol-required therapies including, dexamethasone and tocilizumab (siltuximab may be used if tocilizumab is not available), that are commercially available are not provided or reimbursed by Amgen (except if required by local regulation). The investigator will be responsible for obtaining supplies of these protocol-required therapies.

Dexamethasone mg IV (or equivalent dose of other corticosteroids) will be administered within 1 hour prior to all cycle 1 doses of tarlatamab including all step doses. Dexamethasone dose and schedule may be changed based on emerging safety data.

Additionally, prophylaxis with IV hydration (1L normal saline over 4 to 5 hours) will be administered:

immediately following all tarlatamab doses in cycle 1

Additionally, based upon emerging PK, PD, and safety data in the current study as well as the ongoing FIH study (20160323), the premedication regimen may be modified (including with additional prophylactic therapies) as per the recommendations of the DLRT.

To mitigate the risk of CRS, sites are required to have tocilizumab or siltuximab (if tocilizumab is not available) on site.

6.1.5 Other Intervention Procedures

There are no other treatment procedures in this study.

Protocol Number: 20200439

Date: 05 June 2024 Page 57 of 176

6.1.6 Product Complaints

A product complaint is any written, electronic, or oral communication that alleges deficiencies related to the identity, quality, durability, reliability, safety, effectiveness, or performance of a drug(s) or device(s) after it is released for distribution to market or clinic by either Amgen or by distributors and partners for whom Amgen manufactures the material. This includes all components distributed with the drug, such as packaging drug containers, delivery systems, labeling, and inserts.

This includes any investigational/non-investigational product(s), device(s) or combination product(s) provisioned and/or repackaged/modified by Amgen (ie, tarlatamab and AMG 404) for which Amgen wants to collect complaints.

Any product complaint(s) associated with an investigational product supplied by Amgen are to be reported.

6.1.7 Excluded Treatments, Medical Devices, and/or Procedures During Study Period

The following treatments and/or procedures are excluded within the timeframes specified during the study:

- Other investigational agents
- Concurrent experimental or approved anti-tumor therapies other than study drugs
- Radiation therapy

Exception: radiation therapy for symptom control (eg, bone metastasis) or brain may be allowed after discussion with the Medical Monitor. The radiation therapy should not include the thoracic field and must have been completed at least before the subsequent dose of tarlatamab.

- Immunosuppressive agents with the exception of those required by protocol, treatment for adverse events, CNS metastases, corticosteroid replacement therapy or unless agreed upon by the Principal Investigator and Medical Monitor.
- Any live vaccine therapies. Examples of live vaccines include, but are not limited to, the following: measles, mumps, rubella, chicken pox, yellow fever, rabies, bacille Calmette-Guerin (BCG), and typhoid (oral) vaccine. Seasonal influenza vaccines for injection are generally killed virus vaccines and are allowed. However, intranasal influenza vaccines (eg, Flu-Mist®) are live attenuated vaccines, and are not allowed.
- Subjects must not schedule any major elective surgery during the treatment period and for at least after the last administration of study drugs. If a subject undergoes any unexpected surgery during the course of the study, all study treatments must be withheld, and the investigator or designee should notify the sponsor's medical monitor as soon as possible. A subject may be allowed to resume study drugs if both the investigator and sponsor's medical monitor agree to restart study therapy.

Protocol Number: 20200439

Date: 05 June 2024 Page 58 of 176

6.2 Dose Modification

6.2.1 Dose Cohort Study Escalation/De-escalation and Stopping Rules

6.2.1.1 Dose-Exploration

The dose-exploration part of the study will estimate the recommended phase 2 dose of tarlatamab in combination with AMG 404 using an mTPI2 design. The starting dose and dosing schedule of tarlatamab will be mg as the target dose with 1-step dosing. The planned dose levels are shown in Table 4-1.

6.2.1.2 Dose Level Review Team

[figure not shown]
For the dose exploration phase, a DLRT will convene to review the safety data before recommendations to dose escalate. The required DLRT voting members include the Medical Monitor, Global Safety Officer (GSO), and Site investigator or designee. The DLRT members are responsible for dosing recommendations, which may include implementing step dosing, escalation to the next dose, de-escalation to a lower dose, exploring intermediate dose levels; continuation, delay, or termination of dosing; or repetition or expansion of a cohort; or determination of recommended phase 2 dose. The DLRT will not make dose escalation recommendations until at least 3 subjects enrolled at the dose level are deemed DLT-evaluable. Cumulative adverse events profile will be taken into consideration when making recommendations on dose escalation or de-escalation. See Section 11.3 for more details regarding the DLRT.

Dose Cohort Stopping Rules

For details on dose escalation and stopping rules, refer to Section 4.1.

6.2.1.3 Step Dosing

Due to its known mechanism of action, subjects are at an increased risk for CRS during initiation of tarlatamab treatment. To mitigate this risk, tarlatamab will be administered with the following dosing schedule:

6.2.1.4 Dose-limiting Toxicities

Dose-limiting toxicities are defined as any adverse event with an onset within first following first dose of tarlatamab with any of the following criteria unless clearly related to causes other than tarlatamab:

All grade 3 adverse events except

Protocol Number: 20200439

Date: 05 June 2024 Page 59 of 176

Fatigue lasting less than 7 days

- Grade 3 non-febrile neutropenia that improves to ≤ grade 1 within 3 weeks including the use of growth factor support per neutropenia management guidelines (see Section 6.8.5)
- Endocrinopathies, if manageable with replacement therapy
- Grade 3 nausea/vomiting or diarrhea for less than 72 hours with adequate antiemetic and other supportive care
- Grade 3 amylase or lipase values that are not associated with symptoms or clinical manifestations of pancreatitis
- Grade 3 hematologic lab abnormalities that are not considered clinically relevant
- Grade 3 electrolyte abnormality that lasts up to 72 hours, is not clinically complicated, and resolves spontaneously or responds to conventional medical interventions
- Grade 4 adverse event regardless of duration, except:
 - Grade 4 non febrile neutropenia lasting less than or equal to 7 days including the use of growth factor support per neutropenia management guidelines (see Section 6.8.5)
 - Grade 4 electrolyte abnormality that lasts up to 72 hours, is not clinically complicated, and resolves spontaneously or responds to conventional medical interventions
 - Grade 4 amylase or lipase values that are not associated with symptoms or clinical manifestations of pancreatitis
 - Grade 4 hematologic lab abnormalities that are considered not clinically relevant
- Grade 5 adverse events
- Recurrent grade 2 or higher pneumonitis
- Without exception, any other toxicity requiring permanent discontinuation of AMG 404 per Table 6-2.

The following adverse events will NOT be adjudicated as DLT regardless of the grade or duration:

- Lymphopenia
- Fever
- Tumor lysis syndrome including associated manifestations attributable to TLS (eg, electrolyte abnormalities, renal dysfunction, hyperuricemia)
- 6.2.2 Dosage Adjustments, Delays, Rules for Withholding or Restarting, Permanent Discontinuation

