9.2 Sample Size Determination

Approximately subjects were anticipated to be enrolled in the study (up to subjects in a dose exploration phase, and the remaining subjects enrolled in a dose expansion phase). Study enrollment ended in subjects in Part 1, and subjects in Part 2.

Dose Exploration Phase:

Up to 6 planned dose cohorts will be examined during dose exploration. The planned dose levels for tarlatamab with a fixed dose of AMG 404 (mg IV mg IV are described in Section 4.1.

Dose exploration will begin with subjects treated at Dose Cohort Level 1. The study DLT period is days. Once all subjects enrolled at a certain Dose Cohort Level are DLT evaluable, a DLRT meeting will be convened. Depending on observed safety data, the following may occur: 1) dose de-escalation to the next lowest Dose Cohort Level, 2) additional enrollment to the current Dose Cohort Level, or 3) dose escalation to the next highest Dose Cohort Level or initiation of enrollment in Part 2. In order to consider a certain Dose Level as the recommended phase 2 dose, at least

DLT-evaluable subjects must be enrolled at that Dose Level.

Protocol Number: 20200439

Date: 05 June 2024 Page 106 of 176

These sample sizes are based on practical considerations and are consistent with conventional oncology studies with the objective to estimate the recommended phase 2 dose and to evaluate initial safety and tolerability. The probability of observing at least 1 DLT if the true DLT rate is 10 to 30% is provided in Table 9-1 for various number of subjects.

 Number of Subjects
 10% DLT Rate
 30% DLT Rate

 19
 55

 27
 70

 34
 80

 47
 91

 57
 96

65

Table 9-1. Probability of Observing at Least 1 DLT

DLT = dose-limiting toxicity

Dose Expansion Phase:

If the sample size in the dose expansion phase of 10 (or 20). There is 65% (88%) probability of observing at least 1 adverse event with 10% incidence rate, and the 95% exact confidence interval for 20% objective response (OR) is 3% to 56% (6% to 44%).

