Table 11-6. Schedule of Activities: One-Step Dosing – Cycle 1 Only (AMG 404 Administered

STUDY PERIOD/ **TREATMENT SCR**^a CYCLE Cycle 1 only WEEK^b to -1 DAYb **EOI 757 EOI 404** Pre 757 **EOI 757 EOI 757** Pre 404 168 24 48 24 8 24 တ N 6 N **HOUR** (relative to infusion)d General/Safety Assessments Informed consent Χ Clinical Evaluatione Х Χ Χ Х Х Х Χ Χ Vital signs, pulse Х Χ Χ X^f Х Χ Х Χ X^f Χ Х Χ X^f Χ Χ ox^f 12-lead ECG⁹ Χ Χ Χ Χ Χ ECHO or MUGA Х Adverse event review Serious adverse event review Prior/concomitant medication **Local Laboratory Assessments** CBC with Χ Χ Х Χ Χ Χ Χ Χ Х Χ Χ Χ differential Coagulation Х Χ Χ Χ Χ Х Х Х Chemistry panelh Χ Х Χ Χ Х Χ Х Х Χ Χ Lipase and Х Χ Amylase Urinalysis Х Serum/urine Х Χ pregnancy Testi Safety endocrine Х panel^j CRP Х Χ Χ Χ Χ Χ Χ Χ Χ Χ Χ Χ Х Ferritin Χ X Χ X Χ Х X Χ Х Χ Χ Χ Χ HBsAg, HBcAb, Х HCV Ab, HIV Central and Biomarker Laboratory Tests

Footnotes described after Table 11-9

AMGEN

Protocol Number: 20200439

Date: 05 June 2024 Page 167 of 176

Table 11-6. Schedule of Activities: One-Step Dosing – Cycle 1 Only (AMG 404 Administered Day 8)

	4510 11								 		ə			 	(, ,,,,,,,,,,,,,,,,,,,,,,,,,,,,,,,,,,,,						-,		
STUDY PERIOD/ TREATMENT																							
CYCLE	SCR ^a											Cy	cle 1	only									
WEEK ^b	-3 to -1				1								2 ^c							3			4
VVEEN	to -1				1							4	 							3			4
DAY ^b																							
		70	_						70	m	-	m					п	m					
		Pre:	Ö	N	၈	24	48	96	e'	0	re	0	2	၈	24	48	re	EOI 757	2	ြ	24	48	168
HOUR (relative to infusion) ^d		757	EOI 757			_			Pre 404	EOI 404	Pre 757	EOI 757			_		Pre 757	757			_		 
	er Laborator	y Test	ts (cont	tinued)				1										ı		ı			
	ral and Biomarker Laboratory Tests (continued)																						
Study Drug Administr	ration																						
arlatamab IV																							
nfusion ^t																							
AMG 404 IV																							
nfusion ^t																							
Dexamethasone or			1															1	1				
equivalent ^u		Х									Х						Х						
IV Hydration ^v		1	Х					1	1	1		Х		1	 			Х					
		+			  =====		1	1		 	 		1			 	-		 	1			
Hospital stay ^w			=====	=====										=====	==→		— ==	=====			:==→		

Protocol Number: 20200439

Date: **05 June 2024** Page 168 of 176

Table 11-6. Schedule of Activities: One-Step Dosing – Cycle 1 Only (AMG 404 Administered Day 8)

STUDY PERIOD/ TREATMENT CYCLE	SCR ^a											Cy	/cle 1	only									
	-3																						

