WEEK ^b	to -1				1							2	2 c							3			4
DAY																							
HOUR (relative to infusion) ^d		Pre 757	EOI 757	2	6	24	48	96	Pre 404	EOI 404	Pre 757	EOI 757	2	6	24	48	Pre 757	EOI 757	2	6	24	48	168
Other Assessments																							
MRI Brain ^x	Х																						
Radiological imaging and tumor burden assessment ^y	х																						
			•		•		•							•		•			•		•	Pa	ge 3 of

Protocol Number: 20200439

Date: 05 June 2024 Page 169 of 176

Table 11-7. Schedule of Activities: One-Step Dosing – Cycle 1 Only (AMG 404 Administered

STUDY PERIOD/ TREATMENT CYCLE	SCR ^a											Су	cle 1	only									
WEEK ^b	-3 to -1				1						2	ıc							3				4
DAYb																							
HOUR (relative to infusion) ^d		Pre 757	EOI 757	2	6	24	48	96	Pre 757	EOI 757	2	6	24	48	Pre 404	EOI 404	Pre 757	EOI 757	2	6	24	48	168
General/Safety Assessm			1																				
Informed consent	X																						
Clinical Evaluatione	Х	Χ			L	Χ	Χ	Χ	Χ			L	Χ	Χ	Χ					 	X	Х	Х
Vital signs, pulse oxf	X	Χ	Х		X ^f		Χ	Х	Χ	Χ		X ^f		Χ	Χ	Χ	Χ	X		X ^f	•	Х	X
12-lead ECG ^g	X	Χ	Χ							Χ								Х					
ECHO or MUGA	X																						
Adverse event review			← ==	=====		-====		=====		====	====	====	=====	=====		=====		=====	=====	=====		=====	===→
Serious adverse event review	← =====	====	=====	=====	=====	=====	====		=====					====	=====	=====	====	=====	=====	======	=====	======	===→
Prior/concomitant medication																===→							
Local Laboratory Assess	ments																						
CBC with differential	X	Х				Х	Х	X	Х				Х	Х	Х						X	X	X
Coagulation	Х	Χ				Х		Х	Х				Х		Х						Х		
Chemistry panelh	Х	Х			Х	Х	Х	Х	Х				Х	Х	Х						Х	Х	Х
Lipase and Amylase	X	Х																					
Urinalysis	Х																						
Serum/urine pregnancy Test ⁱ	X	Х																					
Safety endocrine paneli	Х																						
CRP		Χ			Х	Х	Χ		Χ			Χ	Χ	Χ	Χ					Х	Х	Х	Х
Ferritin		Χ			Х	Х	Χ		Χ			Χ	Х	Χ	Χ					Х	Х	Х	Х
HBsAg, HBcAb, HCV Ab, HIV	Х																						
Central and Biomarker L	aboratory To	ests																					

Page 1 of 2

Protocol Number: 20200439

Date: 05 June 2024 Page 170 of 176

Table 11-7. Schedule of Activities: One-Step Dosing – Cycle 1 Only (AMG 404 Administered Day 15)

															`								
STUDY PERIOD/ TREATMENT CYCLE	SCR ^a											Су	cle 1 c	only									
																			3				
WEEK ^b	-3 to -1				1						2	C											4
DAY ^b																							

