DCR is defined as the incidence of a BOR of a confirmed response (CR/PR) or SD while on study as defined by modified RECIST 1.1.

Date: 27 Sep 2024 Page 23 of 51

Duration of Disease Control (DoDC)

The duration of disease control (in month) is defined as time from the earlier date of first dose of tarlatamab or AMG 404 to disease progression or death due to any cause, whichever occurs first. DoDC will be calculated only for subjects with a best overall response of CR, PR or SD.

Subjects will be censored following the censoring strategy described in the analyses of PFS (Appendix C).

Duration of Response (DOR)

The duration of response (in months) is defined as time from first evidence of CR or PR to disease progression or death due to any cause, whichever occurs first. DOR will be calculated only for subjects who achieve a best overall response of PR or CR.

DOR (Months)= (PD / death date - response start date + 1) ×12 / 365.25

Subjects will be censored following the censoring strategy described in the analyses of PFS (Appendix C).

Dose Limiting Toxicity (DLT)

Dose-limiting toxicity (DLT) is defined as tarlatamab-related toxicity with an onset within the first following first dose with the criteria defined in section 6.2.1.4 of the Protocol.

End of Follow-Up

It is defined as when the last subject completes the last protocol-specified assessment in the study.

End of IP administration

End of IP Admin for each subject is defined as the date the decision was made to end IP as recorded on the End of Investigational Product Administration CRF page.

End of Study (Individual Subject)

End of study for each subject is defined as the date when the subject completed protocol-specified last visit shown in the schedule of activities. The date will be recorded on the End of Study CRF page.

Date: 27 Sep 2024 Page 24 of 51

End of Study (End of Trial)

It is defined as the date when the last subject across all sites is assessed or receives an intervention for evaluation in the study (i.e., last subject last visit), including any additional part in the study (eg, long-term follow-up, as applicable.

End of Treatment (EOT)

It is defined as the last assessment per the protocol-specified treatment phase of the study (i.e., end of last treatment cycle) for an individual subject. For subjects who prematurely discontinue investigational product treatment, the EOT should occur as soon as possible (within after a state of investigational product was administered.

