6.3 DLT Analysis Set

For the dose exploration part of the study, the analysis of DLT will be conducted on the DLT Analysis Set, defined as all subjects that are enrolled and received at least 1 dose of tarlatamab or AMG 404 with an evaluable DLT endpoint. The DLT endpoint is evaluable if either: 1) the subject experiences a DLT, or 2) the subject does not experience a DLT and receives tarlatamab or AMG 404 treatment as planned in cycle 1 and has been followed for safety events a minimum of from date of first dose administration of tarlatamab or AMG 404.

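### If AMG 404 first starts on day 8 or 15, the DLT window still runs from the first tarlatamab dose, so those subjects have 7 or 14 fewer days of combination observation and their DLT rate may be understated

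*Protocol*

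**What the plan says.** **DLT window.** Protocol 6.2.1.4 reads "Dose-limiting toxicities are defined as any adverse event with an onset within first following first dose of tarlatamab", and excludes events clearly due to something other than tarlatamab. SAP 5 (Dose Limiting Toxicity) has "tarlatamab-related toxicity with an onset within the first following first dose" and does not name the drug. Protocol 9.2 gives one study-wide period, "The study DLT period is days", with the number blacked out.

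**Evaluability.** Under Protocol 9.3 a DLT-free subject must have received both drugs as planned in cycle 1, with follow-up counted from the start of treatment. SAP 6.3 joins the two drugs with *or* instead of *and*, and requires that the subject be "followed for safety events a minimum of from date of first dose administration of tarlatamab or AMG 404". SAP 10 reports no changes from the protocol's analyses.

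**AMG 404 start day.** Protocol 11.10 has separate cycle 1 schedules headed "AMG 404 Administered Day 8" (Table 11-6) and "AMG 404 Administered Day 15" (Table 11-7). Protocol 1.2 (footnote b), 2.3.3.3 and Table 6-1 present a later AMG 404 day as one response if the combination is not tolerated.

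**Analysis.** DLT incidence is tabulated by planned dose level (Protocol 9.4.2.3.1, SAP 9.6.1). Isotonic regression then uses the observed rate at each dose level, weighted by its sample size (Protocol 9.4.2.5, SAP 3.3). Response, by contrast, is tabulated by dose level and schedule (Protocol 9.4.2.2).

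**The concern.** The primary objective is the safety, tolerability and recommended dose of the combination, and DLTs are one of its endpoints. The DLT list also includes toxicity that forces permanent discontinuation of AMG 404, so AMG 404 toxicity is meant to count. The clock ignores when AMG 404 starts.

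The protocol's own premises give the missing days some weight. Section 6.2.2.2.1 says immune-related toxicity can appear at any time from soon after the first dose to months after the last. Section 2.3.3.3 expects synergistic T-cell activation that may make such toxicity more severe. Because a delayed start is a planned response to poor tolerability, combination observation would be shortest where tolerability is most in doubt. A lower DLT count there could come partly from the shorter combination time, and the planned tables would not show that.

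**Working it through.** **1. Combination time inside the window.** Let D be the blacked-out window length and L the AMG 404 delay. Tables 11-6 and 11-7 give L = 8 − 1 = 7 and L = 15 − 1 = 14 days. Time on both drugs inside the window is D − L, that is D, D − 7 or D − 14 days. This holds for any D longer than 14 days.

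**2. The decision rule.** The mTPI-2 inputs are Beta(1, 1), target 30%, equivalence interval (25%, 33%) and 95% overdose cut-off (Protocol 4.1). From these, the seven blocks of Table 4-2 reproduce in order at n = 3, 4, 5, 6, 7 (or 8), 9 and 10 (or 11). At n = 6 the rule is 0–1 DLT escalate, 2–3 de-escalate, 4 or more unacceptable.

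**3. Effect on the expected rate.** The documents give no figure for this, so three assumptions are needed:
- D between 21 and 42 days;
- constant hazard;
- a 30% DLT risk over a full window on both drugs.

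Let f be the tarlatamab-alone hazard before AMG 404 starts, as a fraction of the combination hazard. Then

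rate = 1 − 0.7^[(D − L)/D + f × L/D].

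For D = 28 and L = 14:
- f = 0: 1 − 0.7^0.5 = 16.3%
- f = 0.5: 1 − 0.7^0.75 = 23.5%
- f = 1: 1 − 0.7^1 = 30.0%

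| D assumed (days) | f | Day 1 | Day 8 | Day 15 |
|---|---|---|---|---|
| 21 | 0 | 30.0% | 21.2% | 11.2% |
| 21 | 0.5 | 30.0% | 25.7% | 21.2% |
| 28 | 0 | 30.0% | 23.5% | 16.3% |
| 28 | 0.5 | 30.0% | 26.8% | 23.5% |
| 42 | 0 | 30.0% | 25.7% | 21.2% |
| 42 | 0.5 | 30.0% | 27.9% | 25.7% |
| any | 1 | 30.0% | 30.0% | 30.0% |

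**4. Effect on the decision at n = 6.** P(0 or 1 DLT) = (1 − p)^6 + 6p(1 − p)^5. This gives 42.0% at p = 30%, 47% at 27.9%, 57.0% at 23.5% and 74.6% at 16.3%.

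**5. A count timed from AMG 404.** If events are counted for D days from the first AMG 404 dose, combination time is D days on every schedule. A 30% combination risk is then seen as 30%, with a 42.0% chance of an escalate row at n = 6.

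**The case against.** Several objections have force.

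- **Tarlatamab-only events still count.** Any qualifying event after the first tarlatamab dose is a DLT. Protocol 2.2.2.3 places cytokine release syndrome mostly after the first two cycle 1 doses, and 6.8.1 points to the first days after the initial infusion. Constant hazard is therefore a simplification, and f = 0 is an extreme. A reader might infer that the DLT rate must fall with no change in toxicity. The documents do not support that: the total may fall little (27.9% against 30% at D = 42, day 8, f = 0.5) or not at all. Delaying AMG 404 may also truly reduce toxicity, and the present window cannot separate that from the artefact.
- **Pooling is not shown.** A reader might infer that start days were mixed in one estimate. The start day for each cohort level is blacked out, so the levels may already separate them. Protocol 9.4.2.1 and SAP 9.1 also allow safety summaries by dose schedule where appropriate. The sections specific to DLTs, however, name dose level only, and the isotonic fit still sets levels against one another.
- **Other safeguards exist.** The review team weighs late-onset events (4.1) and the cumulative adverse event profile (6.2.1.2), and escalation needs a unanimous vote (11.3). DLTs are only one of the primary endpoints. These are real protections, but none changes which events enter Table 4-2 or the isotonic fit.
- **Replacing the window would err the other way.** If the window kept its start but ended D days after AMG 404, total observation would be D + 7 or D + 14 days. At D = 28 and day 15 the expected rate becomes 1 − 0.7^1.25 = 36.0% for f = 0.5 and 1 − 0.7^1.5 = 41.4% for f = 1, both above the 33% limit. A common window from treatment start is a coherent definition for a regimen, so the definition should stay.
- **It may be moot.** Enrollment ended in January 2023 (Protocol 4.1), AMG 404 is no longer supplied (Table 6-1), and the visible text does not say that anyone started AMG 404 late.

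**Conclusion.** The point holds in a limited form. For a subject who starts AMG 404 on day 8 or 15, combination observation inside the DLT window is 7 or 14 days shorter than for a day-1 start, and no passage compensates. Because the DLT tables and isotonic regression are specified by dose level only, rates from different combination exposure times may be compared or combined without the reader knowing. The DLT rate of a delayed schedule may therefore be understated relative to a day-1 start.

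The loss of days follows from the text. The size of any understatement does not: it depends on the blacked-out window length, the tarlatamab-alone hazard and the timing of onset. Under the stated assumptions at 28 days, a 30% risk would appear as 16.3% to 30.0% on the day-15 schedule. If no subject started late, there is no effect.

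**What to change.** 1. Keep the protocol's DLT definition and the counts used at the dose level reviews.
2. In SAP 9.6.1, tabulate DLTs by dose level and AMG 404 start day. Do not pool start days in one isotonic estimate without also showing them separately.
3. For any subject who started AMG 404 on day 8 or 15, add a supplementary count of events meeting the DLT criteria within the stated number of days after the first AMG 404 dose. Show tarlatamab-only events before that dose separately, and label the table post hoc.
4. Reconcile the DLT analysis set in SAP 6.3 (either drug) with Protocol 9.3 (both drugs).
5. If no subject started AMG 404 late, replace items 2 and 3 with one sentence saying so.

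The cost is SAP wording, one extra table and some re-review of events against DLT criteria that involve judgement. Adverse events are already collected to the second safety follow-up visit or 60 days after the last dose, whichever is later (Protocol 8.4.9.1.1), so no new data collection should be needed. The reported DLT rate for a delayed schedule may turn out less favourable.
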